	never) to 4 (extreme or always). A higher score indicates worse
	pain, stiffness, or functional limitation.
	The EuroQol-5 Dimensions
	The EuroQol-5 Dimensions (EQ-5D) is a validated instrument
	which assesses an individual's current health status and heath
	related quality of life. The EQ-5D-3L descriptive component
	assesses five dimensions: mobility, self-care, usual activities,
	pain/discomfort, and anxiety/depression over three levels of
	severity. The EQ visual analogue scale (EQ VAS) assesses the
	respondent's self-rated overall health state on a scale from 0 (worst
	imaginable health state) to 100 (best imaginable health state).
	Numeric Rating Scale
	The NRS is a validated measure of knee pain. The NRS is an 11
	point Likert type scale anchored by 0 "no pain" and 10 "worst
	possible pain". Subjects rate their average pain over the last 48
	hours.
	Patient Preference Questionnaire
	Patient preferences are concerned with determining patient-related
	factors such as patients' adherence to treatment, patients'

	satisfaction with treatment, and health outcomes. Patient
	preferences will be measured utilizing questions to elicit patients'
	preferences following their knee OA treatment.
	Resource Utilization and Costing
	Health economics will be evaluated throughout the study.
	Healthcare resource utilization for each subject will be recorded to
	capture information about healthcare costs following index
	treatment with nSTRIDE APS or HA and follow-up.
Imaging	Radiographs
Assessment	Standing posterior-anterior (PA) fixed flexion knee radiographs (X-
Tools:	rays) are used to assess structural features of the joint, including
	joint space width, and presence or absence of subchondral
	sclerosis, subchondral cysts, and osteophytes. X-ray assessments
	will be performed by a core imaging laboratory.
Primary Endpoint:	The primary endpoint will be the change in pain from baseline to 12
	months following injection of nSTRIDE APS or HA, as measured by
	the WOMAC LK 3.1 pain subscale.
Primary Hypothesis	H ₀ : μ _{APS} = μ _{HA} vs H ₁ : μ _{APS} ≠ μ _{HA}
Primary Hypothesis for nSTRIDE	H ₀ : μ _{APS} = μ _{HA} vs H ₁ : μ _{APS} ≠ μ _{HA}
Primary Hypothesis for nSTRIDE Superiority Testing:	H ₀ : $\mu_{APS} = \mu_{HA} vs H_1: \mu_{APS} \neq \mu_{HA}$ Where:
Primary Hypothesis for nSTRIDE Superiority Testing:	H ₀ : $\mu_{APS} = \mu_{HA} vs H_1: \mu_{APS} \neq \mu_{HA}$ Where: H ₀ is the Null Hypothesis

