arm (i.e. patients with clinically meaningful improvement in
WOMAC Pain score, inclusive of originally assigned and cross-
over patients)
 Average number of cumulative interventions per patient
• Time from the initial injection (nSTRIDE APS or HA) to
subsequent injection(s), cross-over, or study exit for other
invasive treatment
 Resource utilization for index knee OA.

⁶ Clinically meaningful improvement is considered to be an improvement of at least 20% from baseline

	The following endpoint will be assessed annually in the long-term
	follow-up phase for patients that have crossed over:
	Percentage of patients preferring each treatment due to:
	1. Greater pain relief
	2. Longer lasting pain relief
	3. Greater improvement in function
	4. Longer lasting improvement in function
	5. Fewer post-injection side effects
Safety Endpoints	Occurrence of all AEs up to 12 month time-point and
	occurrence of AEs of interest across all post-operative time
	points

This Clinical Investigation Plan is written in accordance with ISO14155:2011 "Clinical Investigation of medical devices for human subjects – Good clinical practice" (40). The Adverse Events sections is written in accordance with the ISO14155:2020 "Clinical Investigation of medical devices for human subjects – Good clinical practice" (41).

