# 1.2 Study Design

The study is a two-phase, randomized, double-blind study with a planned enrollment of 246 subjects assigned to treatment groups on a 1:1 basis. It is designed to determine whether APS provides a more effective treatment for knee osteoarthritis than HA. The study will be conducted in two phases. Phase I is the randomized, double-blind portion of the study. After each subject completes all 12 month follow-up evaluations, only subjects will be blinded to the individual treatment allocation resulting in single-blind design following 12-month follow-up time point. Subjects from both groups will be able to request additional injections of their originally assigned treatment as frequently as needed, provided they did not experience any significant clinical concerns after previous treatment administrations and are benefiting from it, as determined by the investigator. During the long-term follow-up phase (12 -60 months), subjects may also elect to cross over to the other treatment arm and receive additional injections of the other treatment as frequently as needed, provided they did not experience any significant clinical concerns after previous treatment administrations and are benefiting from it, as determined by the investigator. Subjects may only cross over from their originally assigned treatment group to the other treatment group one time during the study.

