#### Treatment Success from Original Treatment Assignment

- (1) No cross-over or study exit for other invasive treatment
- (2) Clinically meaningful improvement in WOMAC Pain score (>20% from baseline)

The items in **Table 7** will be analyzed according to the original treatment assignment (APS or HA). The items in **Table 8** will use Treatment / Crossover group as the predictor variable: (1) randomized to APS and not crossed over to HA, (2) randomized to APS and crossed over to HA, (3) randomized to HA and crossed over to APS and (4) randomized to HA and not crossed over to APS. For all tests where the Treatment / Crossover Group is the predictor variable, patients progressing to other invasive treatment for their OA will be included as a Non-Responder (where OMERACT-OARSI responder is the outcome variable) or using the most recently collected outcome score (where pain, function or EQ-5D is the outcome variable).

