# Table 8 - Planned Phase II Statistical Analysis – Treatment/Crossover Group

Predictor Variable	Outcome Variable(s)	Statistic	Expected Outcome
Treatment / Crossover Group	Progression to other invasive OA treatment	Chi-Square	Trend APS Superior

Treatment / Crossover Group	OMERACT-ORSI Responder / Non- Responder	Chi-Square	Trend APS Superior
Treatment / Crossover Group	WOMAC Pain, 6 Mo Intervals	One-Way Anova	Trend APS Superior
Treatment / Crossover Group	WOMAC Function, 6 Mo Intervals	One-Way Anova	Trend APS Superior
Treatment / Crossover Group	NRS Pain, 6 Mo Intervals	One-Way Anova	Trend APS Superior
Treatment / Crossover Group	EQ-5D Global Assessment 6 Mo Intervals	One-Way Anova	Trend APS Superior
Treatment / Cross Over Group	Patient Preference	Chi-Square	Trend APS Superior
Treatment / Cross Over Group	WOMAC Pain Δ: Baseline-12M	Summary Statistics and ANCOVA Model*	Trend APS Superior
Treatment / Cross Over Group	WOMAC Pain ∆: Baseline-6M	Summary Statistics and ANCOVA Model*	Trend APS Superior
Treatment / Cross Over Group	Percent of Subjects in each Treatment/Cross Over Category	Chi-Square	Trend APS Superior

\*Analysis of Covariance models will be used in order to determine if changes in WOMAC Pain score from Baseline to12 months (first model) or from 6 to 12 months (second model) differ according to what type of 2nd injection they chose to receive ( $\beta_3$ ), and whether this difference varies for APS and HA ( $\beta_2$  \*  $\beta_3$ ). The model will be as follows:

 $Y=\beta_0+\beta_1+\beta_2+\beta_3+\beta_2*\beta_3$ 

Where

 $\beta_0$ = Intercept

 $\beta_1$ = Baseline WOMAC Pain score

 $\beta_2$  = Treatment Group

 $\beta_3$ = 2nd Injection (None, Same, Crossover)

Y= Change in WOMAC Pain

In addition to these tests, results of the patient preference questionnaire will be tabulated by crossover group.

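### The Table 8 chi-square on patient preference compares the two crossover sequences, so on the protocol's outcome it can neither support nor refute preference for APS

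*SAP*

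**What the plan says.** SAP section 4.5 states that the Table 8 items use Treatment / Crossover group as predictor. Its four levels are "1) randomized to APS and not crossed over to HA, (2) randomized to APS and crossed over to HA" and "3) randomized to HA and crossed over to APS and (4) randomized to HA and not crossed over to APS". The preference row of Table 8 reads "Patient Preference Chi-Square Trend APS Superior". It gives no definition of the preference variable, no restriction of the population, and no choice among questions or visits. The text after the table adds that "results of the patient preference questionnaire will be tabulated by crossover group".

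The protocol synopsis (Exploratory Endpoints, long-term part) is more specific. The endpoint is assessed annually in the long-term "follow-up phase for patients that have crossed over". It is defined as "Percentage of patients preferring each treatment due to" each of five reasons: greater pain relief, longer-lasting pain relief, greater functional improvement, longer-lasting functional improvement, and fewer side effects after injection.

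SAP section 1.2 limits crossover: "Subjects may only cross over from their originally assigned treatment group to the other treatment group one time during the study". There are therefore exactly two sequences in which a patient receives both treatments.

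**The concern.** Under the protocol's definition, the two groups that never crossed over are outside the preference endpoint. The four-group table then reduces to two rows (APS then HA, HA then APS) by treatment preferred.

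A chi-square on that table has as its null hypothesis that the proportion preferring APS is the same in both sequences. A uniform preference for APS satisfies this null. A tendency to prefer the later treatment, or the earlier one, violates it even when neither product is favoured. The stated expectation of a trend towards APS is therefore not something the test can show.

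Both documents name patient preference among the matters on which the long-term phase is to examine superiority of APS. A p-value from this row could be read as evidence on that question in either direction, and neither reading would be justified.

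**Working it through.** The documents give no sample size, expected rate or power for preference, so there is no planned figure to reproduce. The number of crossovers and the preference rates below are assumptions, shown over a range. The 0.05 level is the SAP's for Phase II analyses (section 1).

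**What each coding tests.** Let p2 and p3 be the probability of preferring APS in the APS-to-HA and HA-to-APS groups. Write τ for a treatment effect on preference and ω for a tendency to prefer the later treatment:

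- p2 = 0.5 + τ − ω and p3 = 0.5 + τ + ω, so p3 − p2 = 2ω. The treatment effect cancels.
- If the outcome is instead preference for the second-received treatment, the probabilities are q2 = 1 − p2 = 0.5 − τ + ω and q3 = p3 = 0.5 + τ + ω, so q3 − q2 = 2τ. The common order effect cancels.

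**Two worked tables, 20 patients per sequence.** Pearson chi-square = N(ad − bc)² / (product of the four margins).

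- 75% prefer the later treatment and there is no treatment effect. Prefer APS / prefer HA is 5/15 and 15/5. Chi-square = 40 × (25 − 225)² / 20⁴ = 10.0, p = 0.0016, yet 20 of 40 prefer APS.
- 80% prefer APS in both sequences. The table is 16/4 and 16/4, so chi-square = 0 and p = 1.0, yet 32 of 40 prefer APS (exact binomial against 50%, p = 0.00018). Recoded as first / second preferred, the same answers are 16/4 and 4/16, giving 40 × (256 − 16)² / 20⁴ = 14.4, p = 0.00015.

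**Rejection rates by exact enumeration**, two-sided chi-square without continuity correction. Table 7 of the SAP expects more HA than APS patients to cross over, so unequal groups are included.

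| Crossed over (APS-to-HA / HA-to-APS) | APS preferred by 80% in both | Order effect only (APS preferred by 30% and 70%) |
|---|---|---|
| 10 / 20 | 3.7% | 57.5% |
| 20 / 20 | 5.0% | 71.3% |
| 20 / 40 | 4.7% | 86.3% |
| 40 / 40 | 5.1% | 96.4% |
| 60 / 60 | 5.0% | 99.6% |

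With APS preferred by 70% to 90% in both sequences, rejection stays between 3.7% and 5.9% at all these sizes. An order effect favouring the earlier treatment gives the same figures as one favouring the later. At 20/40 the recoded chi-square rejects 99.8% of the time in the 80% scenario and 5.1% under the pure order effect.

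**Pooling is not a safe substitute.** At 20/40 with a pure order effect, the expected number preferring APS is 20 × 0.30 + 40 × 0.70 = 34 of 60 (57%), although neither treatment is favoured. An exact pooled test against 50% then rejects 10.2% of the time.

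**Limit of the recoding.** If the tendency to prefer the later treatment differs between sequences (ω2 and ω3), then q3 − q2 = 2τ + (ω3 − ω2). Suppose τ = 0, but 60% of APS-to-HA and 85% of HA-to-APS patients prefer the second treatment because different kinds of patient chose to cross over. The recoded difference is then 25 points. Fisher's Exact test rejects about 32% (20/20), 50% (20/40) or 64% (40/40) of the time.

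**The case against.** The strongest reply is that the SAP does not fix the coding. If the variable were first-received against second-received treatment preferred, the same chi-square on the two crossed-over groups would respond to treatment preference. This stands as a limit: a reader might infer that the SAP demonstrably tests order, and the documents do not go that far. But the only definition of the endpoint, in the protocol, is the percentage preferring each treatment. On that definition the test fails as shown, and the other coding appears nowhere.

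Three further inferences are tempting and not supported.

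- *Preference data are collected only from patients who crossed over.* The synopsis limits assessment of the endpoint. Its general description of the questionnaire refers to "preferences following their knee OA treatment" without that limit, and the data-collection table is not in the text reviewed. If other patients were asked, they would have received only one of the two study treatments, and a four-group comparison would still not test whether APS is preferred.
- *Patients cross over because the first treatment failed them.* The crossover rules call it elective and give no such motive. The size and direction of any order effect are unknown.
- *Recoding isolates APS against HA.* It does so only if the sequences are comparable apart from treatment order, and self-selection may prevent that.

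It is also fair to say that the planned tabulation by crossover group would show a strong uniform preference, and that the analysis is exploratory and unadjusted. The tabulation is additional to the test, however, and does not correct the inference attached to it.

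**Conclusion.** The concern holds on the protocol's own outcome. The planned chi-square compares the proportion preferring APS between the two crossover sequences. It responds to differences in order or selection and rejects at about the alpha level when APS is preferred equally in both. A significant result would not show preference for APS, and a non-significant one would not rule it out.

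The cancellation of the treatment effect follows from the null hypothesis when preference is equal in both sequences. The percentages depend on assumed crossover numbers and preference rates, though the pattern was the same at every size tried. The conclusion also assumes that the SAP means the protocol's coding, which it should state. The consequence is confined to one exploratory Phase II row; the primary and secondary conclusions are not affected.

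**What to change.** Revise the preference row of Table 8 as follows.

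- Restrict it to groups 2 and 3.
- Define the outcome, including how a no-preference answer is handled, for each of the five reasons and at each annual visit.
- Make the main result the percentage preferring APS, with a 95% CI, in each sequence.
- If a test is kept, code the outcome as second-received against first-received treatment preferred and compare the two sequences by Fisher's Exact test.
- State that this contrast removes only an order effect common to both sequences, that crossover is elective so the sequences may differ by self-selection, and that the result is exploratory and applies only to patients who chose to cross over.

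The cost is SAP wording for one row and a more limited conclusion. The outcome as the protocol defines it needs no new data.

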# Table 7. Planned Phase II Statistical Analysis-Originally AssignedTreatment

Predictor Variable	Outcome Variable(s)	Statistic	Expected Outcome
Treatment Group	Election to Cross Over	Fisher's Exact	Statistically Significant, More HA than APS Cross Over
Treatment Group	Percentage of patients achieving	Fisher's Exact	APS Superior

	treatment success from initial injection		
Treatment Group	Percentage of patients achieving treatment success from originally assigned treatment	Fisher's Exact	APS Superior
Treatment Group	Percentage of patients achieving success in each treatment arm (i.e. patients with clinically meaningful improvement in WOMAC Pain score, inclusive of originally assigned and cross-over patients)	Fisher's Exact	APS Superior
Treatment Group	Average number of cumulative interventions per patient	Likelihood Ratio Chi-Square	Trend APS Superior
Treatment Group	Time from the initial injection (nSTRIDE APS or HA) to first subsequent injection, cross- over, or study exit for other invasive treatment	Kaplan Meier – Time to first subsequent injection/cross- over/other invasive treatment	Trend APS Superior

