An X-ray will be obtained at 12 months and annually thereafter to assess anatomical changes. Only radiograph images taken up to 24 months of follow-up will be transferred to the Core Imaging Laboratory for independent review. Image acquisition, transfer, and analysis procedures will be performed using validated, prospectively defined methods. All AEs that occur during the 12 month blinded study period will be recorded. In the long-term follow-up phase (12 - 60 months), only events of interest will be recorded.

After each subject completes all 12-month follow-up evaluations, only subjects will be blinded to the individual treatment allocation resulting in single-blind design following 12-month follow-up time point. Subjects from both groups will be able to request additional injections of their originally assigned treatment as frequently⁴ as needed, provided they did not experience any significant clinical concerns after previous treatment administrations and are benefiting from it, as determined by the investigator. During the long-term follow-up phase (12 - 60 months), subjects may also elect to cross over to the other treatment arm and receive additional injections of the other treatment as frequently as needed, provided they did not experience any significant clinical concerns after previous treatment administrations and are benefiting from it, as determined by the investigator. Subjects may only cross over from their originally assigned treatment group to the other treatment group one time during the study. Subjects seeking alternative invasive OA treatment in the index knee who do not wish to cross over or who have already crossed over will exit the study, and their selected treatment option will be recorded.

⁴ Please refer to Synvisc One IFU for specified clinical use requirements.

Study Duration:	Maximum study duration per subject is 62 months: 60 r	nonths from
	treatment to last follow-up, and two additional mo	onths if the
	maximum visit window time is realized.	
Inclusion Criteria:	1. Male or female at least 18 years of age at time of	f screening.
	2. Willingness and ability to comply with study proc	cedures and
	visit schedules and able to follow oral a	and written
	instructions.	
	3. A standing knee radiograph showing a K-L gra	de of 2 to 4
	and an absence of severe osteoarthritis	defined as
	advanced stage osteoarthritis, including large o	steophytes,
	chronic fractures or bone remodeling, severe	deformity or

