# 4.4.2 Exploratory Outcomes (Imaging)

X-rays are evaluated for Kellgren-Lawrence (K-L) grade and absence of severe osteoarthritis by the central laboratory for confirmation of eligibility.

Post-injection X-rays taken at 12 months will receive K-L grades that will be compared to baseline. For each subject, results will be categorized as (1) worse—a higher Kellgren-Lawrence grade at 12 months compared to baseline, (2) no change in grade from baseline to 12 months or (3) Improvement—a decrease in grade from baseline to 12 months. An analysis of the percentage of subjects in each treatment group who fall into each of these three categories will be done using a Likelihood Ratio Chi-square test. This test will also be repeated within subgroups defined by the baseline K-L grade.

Measurements of medial and lateral Joint Space Width (JSW) will be performed to assess narrowing over time in the medial and lateral compartments of the treated joint. Joint Space Narrowing (JSN) will be calculated for each compartment as the change in JSW between the 12 Month visit and the Baseline visit.

A list of planned statistical tests on imaging data is presented in **Table 6**. All tests will be conducted at  $\alpha$  = 0.05 and will not be adjusted for multiple comparisons as these are exploratory outcomes. In addition to these tests, logistic regression will be used to determine whether imaging results are associated with OMERACT-OARSI categorization.

Variable	Test
X-ray	
Change in K-L	Likelihood Ratio Chi-Square
Change in K-L by baseline K-L grade	Likelihood Ratio Chi-Square for each subgroup

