# 7. Data Collection Time Points

Data will be collected at the screening visit, the injection visit, and at 1, 3, 6 and 12 months following the injection. After each subject completes all 12 month follow-up evaluations (Phase I), individual treatment allocation will be unblinded to the investigators. From this time-point on, only subjects will be blinded to study treatments resulting in a single-blind design during the longterm follow-up period (Phase II). During Phase II of the study, the subject may opt to get additional injections of their originally assigned treatment, or they may opt to crossover to the other treatment group and may receive multiple injections of the crossover treatment. Subjects may only crossover one time during the study. In Phase II, follow-up visits will occur at six month intervals until five years following the initial injection.

The follow-up visits will preferably be completed during an office visit to ensure subject compliance, but this is not mandatory and follow-up visits may consist of a structured telephone interview or electronic self-report with exception of annual visits at which radiograph is to be taken. The investigative center will contact the subject to complete the Follow-up and AE forms. The subject will be asked to complete a Patient Questionnaire.

A table showing the data collected at each time interval is presented in the study protocol.

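### The exploratory mean number of interventions per patient is tested with an unordered chi-square that does not compare means and ignores time in study

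*SAP*

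**What the plan says.** SAP section 4.5, Table 7, lists the outcome "Average number of cumulative interventions per patient" with the statistic "Likelihood Ratio Chi-Square" and an expected trend in favour of APS. The text before the table says that its items "will be analyzed according to the original treatment assignment (APS or HA").

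Three design features bear on this count:

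- **Accrual.** In the long-term phase subjects may "request additional injections of their originally assigned treatment as frequently as needed" (SAP section 1.2), and may cross over once. There is no fixed number of injections.
- **Length.** SAP section 7 says that "follow-up visits will occur at six month intervals until five years following the initial injection".
- **Exit.** The protocol synopsis (Study Design and Procedures) says that subjects seeking other invasive treatment of the index knee "who do not wish to cross over or who have already crossed over will exit the study".

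The SAP gives no person-time denominator, offset, censoring rule or exit rule for this count, and does not define an intervention. Its rule for patients who progress to invasive treatment is confined to analyses by Treatment / Crossover group, and there to responder status and scores.

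**The concern.** There are two separate problems.

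First, the test does not match the endpoint. The endpoint is a mean count. Elsewhere the SAP uses the likelihood-ratio chi-square for categories of subjects; for change in K-L grade, for example, the percentages of subjects "who fall into each of these three categories will be done using a Likelihood Ratio Chi-square test". Applied to counts, it asks whether the two distributions differ in any way. It ignores the order of 0, 1, 2 and 3, yields no estimate, and cannot itself show the direction that Table 7 expects.

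Second, the count depends on time in study, and one route out of the study is tied to treatment failure. If more subjects exit from one arm, that arm has less time in which to record injections. A difference in the count could then reflect follow-up rather than need for treatment, or a real difference could be hidden. Injection frequency is a named objective of the long-term phase, so the row will be read.

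**Working it through.** The documents give no expected count, rate or power for this endpoint, so there is no figure of theirs to reproduce. The injection and exit rates below are assumptions. From the documents come 123 subjects per arm and a long-term phase from month 12 to month 60, that is T = 4 years.

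**Step 1. Mean counts when injection rates are equal.** Assume r = 0.5 injections per year in both arms, and that a fraction p exits at year 1 of the phase.

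Mean follow-up = (1 − p) × 4 + p × 1; mean count = r × mean follow-up.

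- HA, p = 0.30: 0.7 × 4 + 0.3 × 1 = 3.1 years; 0.5 × 3.1 = 1.55
- APS, p = 0.10: 0.9 × 4 + 0.1 × 1 = 3.7 years; 0.5 × 3.7 = 1.85
- Apparent gap: 1 − 1.55/1.85 = 16%

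**Step 2. Dependence on the definition.**

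| What counts | HA | APS | Gap |
|---|---|---|---|
| Further injections only | 1.55 | 1.85 | 16% |
| Plus treatment at exit (+0.30, +0.10) | 1.85 | 1.95 | 5% |
| Plus initial injection (+1 each) | 2.85 | 2.95 | 3% |

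Per year of follow-up, with the treatment at exit counted: HA 1.85/3.1 = 0.60, APS 1.95/3.7 = 0.53. The order of the arms reverses once time is used.

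**Step 3. How often the tests reject.** Poisson injections, 123 per arm, counts grouped 0, 1, 2, 3, 4+, two-sided 0.05, injection rates equal at 0.5 per year. The comparator is a Poisson test on injections with a log follow-up offset.

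| Exit at year 1 (HA vs APS) | Chi-square, injections only | Chi-square, exit counted | Offset test |
|---|---|---|---|
| 30% vs 10% | about 28–32% | about 15% | about 5% |
| 20% vs 10% | about 10% | about 7% | about 5% |

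A harsher case has exponential exit at 0.3 (HA) and 0.1 (APS) per year. Over four years 1 − exp(−1.2) = 70% and 1 − exp(−0.4) = 33% leave. The chi-square rejects in 66% of trials and the offset test in 5%.

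**Step 4. A real difference can be hidden.** With the same exponential exit and rates of 0.35 (APS) and 0.5 (HA) per year, the true ratio is 0.5/0.35 = 1.43, yet mean counts are 1.16 and 1.17. Power is 15% for the chi-square and 85% for the offset test.

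**Step 5. Equal exit.** With 10% exit in both arms the chi-square holds its level (about 5%) but loses power. For rates of 0.5 and 0.4 per year it detects the difference in about 36% of trials, against about 63% with the offset model. This loss does not depend on exit.

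**The case against.** The strongest reply has five parts.

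- **Status.** All long-term endpoints are exploratory at an unadjusted 0.05, and Table 7 expects only a trend here. This stands. A reader might infer that a main durability endpoint, or the durability conclusion itself, could be reversed. The documents do not support that. The Kaplan-Meier row counts exit for invasive treatment as an event, both treatment-success definitions require its absence, and Table 8 analyses progression to invasive treatment directly. An arm with more failures would look worse in all of these.
- **Direction.** A reader might also infer that the worse arm must show fewer interventions. That does not follow. Exit applies only to subjects who seek other invasive treatment and either decline cross-over or have used it. Other dissatisfied subjects may cross over and receive more injections, which raises the count. The illustration leaves this mechanism out.
- **Size.** The gap shrinks from 16% to 5% or 3% with the definition, and the 66% figure needs 70% exit in one arm. This stands, which is why the range is shown.
- **Common time points.** The protocol has the endpoint assessed at each long-term visit, which fixes nominal time from injection. It does not say how exited subjects are counted. Restricting to those still in study would select on outcome.
- **Remedy.** A log-time offset corrects for unequal time only if exit is unrelated to a subject's injection rate. The 5% for the offset test comes from simulations in which that holds. It is also a rate, not the average cumulative number named in the plan. This stands and shapes the fix.

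None of this gives the chi-square an order, an estimate of the mean or a time basis.

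**Conclusion.** The point holds as a minor one. As written, Table 7 tests a mean count with a method that does not compare means and ignores time in study, and the SAP does not say how exited subjects enter the count. The mismatch of test and endpoint follows from the documents alone, and it costs power even when exit is equal.

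Distortion from unequal exit is a possibility, not a finding. Its direction and size depend on injection and exit rates that the documents do not give, on how many failing subjects cross over instead of leaving, and on what counts as an intervention. Under the central assumptions (0.5 injections per year in both arms, exit of 30% versus 10% at year 1), the gap is 16%, or 5% with the treatment at exit counted. False signals of different injection frequency then arise in about 28–32% of trials, or about 15%. With 20% versus 10% exit these fall to about 10% and 7%. The primary conclusion and the other durability analyses are not affected.

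**What to change.** Amend SAP section 4.5 and the Table 7 row as follows:

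1. Define an intervention: whether the initial injection counts, whether injections after cross-over count towards the randomised arm, and whether the invasive treatment at exit counts.
2. Replace the chi-square with a negative binomial (or over-dispersed Poisson) regression of the count on randomised arm, with log follow-up time as offset. Report the rate ratio with its 95% confidence interval.
3. Because the offset does not deal with informative exit, also report the mean cumulative count over time by arm, with exit for invasive treatment as a terminal event and other losses censored. This keeps the average number per patient that the endpoint names. Accrual still stops at exit (in the illustration it would again give 1.55 and 1.85 for injections alone), so show the number of exits by arm beside it.

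The cost is SAP wording and a little more analysis. No new data should be needed, since the planned time-to-event endpoint already requires injection and exit dates. The downside is that a rate-based estimand will sit alongside the mean count, and the text must say how the two are read together.
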